## **5.2 Administrative Procedures/Assessments**

### **5.2.1 Informed Consent**

It is the responsibility of the Investigator / designee to give each patient, prior to inclusion in the trial, full and adequate verbal and written information regarding the objective and procedures of the trial and the possible risks involved. Sufficient time should be allowed for the patient to decide on trial entry. Patients must be informed about their right to withdraw from the trial at any time. Written patient information must be given to each patient before enrolment. The written patient information is an approved patient information sheet (PIS) according to national guidelines.

The Investigator must obtain documented written informed consent from each potential patient prior to participating in a clinical trial. Consent must be documented by the patient's dated signature on a consent form along with the dated signature of the person conducting the consent discussion. If the patient is illiterate, an impartial witness should be present during the entire informed consent reading and discussion. Afterwards, the patient should sign and date the informed consent, if capable. The impartial witness should also sign and date the informed consent along with the individual who read and discussed the informed consent. Only the Chief Investigator (CI), Co-Investigators and those Sub-Investigator(s) delegated responsibility by the CI, having signed the delegation of responsibilities log, are permitted to gain informed consent from patients and sign the consent form. All signatures must be obtained before the occurrence of any medical intervention required by the protocol.

A copy of the signed and dated consent form should be given to the patient before participation in the trial. The original consent form should be stored in the site file with a copy also being placed in the patient's medical notes. Results from tests conducted as part of patients' standard care may be used as part of screening to determine eligibility as long as the tests were conducted within the acceptable time window.

The initial informed consent form, any subsequent revised written informed consent form and any written information provided to the patient must receive the REC approval/favourable opinion in advance of use. The patient should be informed in a timely manner if new information becomes available that may be relevant to the patient's willingness to continue participation in the trial. The communication of this information will be provided and documented via a revised consent form or addendum to the original consent form that captures the patient's dated signature. The informed consent will adhere to REC requirements, applicable laws and regulations.

### **5.2.2 Inclusion/Exclusion Criteria**

All inclusion and exclusion criteria will be reviewed by the Investigator or qualified designee to ensure that the patient qualifies for the trial.

### **5.2.3 Demographic Data, Medical History and Treatment History**

Demographic data collected will include date of birth and race/ethnicity. A medical history will be obtained by the Investigator or qualified designee. Medical history will include all active conditions, and any condition diagnosed within the prior 10 years that are considered to be clinically significant by the Investigator. Details regarding the disease for which the patient has enrolled in this study will be recorded separately and not listed as medical history. In addition to the medical history the Investigator or qualified designee will obtain details the patient's current disease status and treatment history including prior and current details regarding disease status, in addition to all prior cancer treatments including systemic treatments, radiation and surgeries.

### **5.2.4 Subsequent Anti-Cancer Therapy Status**

Patients that discontinue from pembrolizumab for any other reason than disease progression will have a follow-up visit every 9 weeks in which the Investigator should review all new anti-cancer therapy initiated after the last dose of pembrolizumab. If a patient initiates a new anti-cancer therapy within 30 days after the last dose of trial treatment, the 30 day Safety Follow-up visit must occur before the first dose of the new therapy. Once new anti-cancer therapy has been initiated the patient will move into survival follow-up.

### **5.2.5 Survival Status**

The Investigator or qualified designee will assess the patient for survival status. The assessment will include the patient status and if applicable details of patient death or detail if patient has been lost to follow-up.

### **5.2.6 Prior and Concomitant Medications Review**

#### **5.2.6.1 Prior Medications**

The Investigator or qualified designee will review prior medication use, including any protocol-specified washout requirement, and record prior medication taken by the patient within 28 days before starting the trial. Treatment for the disease for which the patient has enrolled in this study will be recorded separately and not listed as a prior medication.

#### **5.2.6.2 Concomitant Medications**

In addition the investigator or qualified designee will record all medication, if any, taken by the patient during the trial. All medications related to reportable SAEs and events of clinical interest (ECIs) should be recorded as defined in Section 7.

## **5.3 Clinical Procedures/Assessments**

### **5.3.1 PD-L1 Assessment**

To participate in the trial patients need available tissue of a tumour lesion not previously irradiated (tumours progressing in a prior site of radiation are allowed) for PD-L1 characterisation. This specimen will be evaluated at a central laboratory for expression status of PD-L1 using PD-L1 IHC 22C3 pharmDx (Dako) assay. If no tissue is available then following informed consent they should undergo a biopsy of a tumour lesion for biomarker analysis. NOTE: Patients participating in this trial will be unselected for their PD-L1 status.

### **5.3.2 Adverse Event (AE) Monitoring**

The investigator or qualified designee will assess each patient for potential new or worsening AEs as specified in the schedule of study assessments (Table 3) and more frequently if clinically indicated. AEs will be graded and recorded from confirmation of entry into the trial until the patients 30 day safety follow up visit according to NCI CTCAE v4.0 (see Appendix 4). Toxicities will be characterised in terms regarding seriousness, causality, toxicity grading, and action taken with regard to trial treatment.

All AEs of unknown aetiology associated with pembrolizumab exposure should be evaluated to determine if it is possibly an event of clinical interest (ECI) or a potentially an immune-related adverse event (irAE). See Appendix 5 and the separate ECI guidance document regarding the identification, evaluation and management of AEs of a potential immunological aetiology. Please refer to section 7 for detailed information regarding the assessment and recording of AEs.

### **5.3.3 MRC dyspnoea Score**

The investigator or qualified designee will assess the patient's dyspnoea using the MRC Dyspnoea Score (Appendix 2) at screening period and the time points defined in the study schedule of assessments (Table 3).

### **5.3.4 Full Physical Exam**

The investigator or qualified designee will perform a complete physical exam at screening period and the time points defined in the study schedule of assessments (Table 3). Clinically significant abnormal findings should be recorded as AEs during the trial.

### **5.3.5 Directed Physical Exam**

For cycles that do not require a full physical exam as described in the schedule of assessments (Table 3), the investigator or qualified designee will perform a directed physical exam as clinically indicated prior to trial treatment administration.

### **5.3.6 Vital Signs**

The investigator or qualified designee will take vital signs at screening, prior to the administration of each dose of trial treatment and at treatment discontinuation as specified in the schedule of study assessments (Table 3). Vital signs should include temperature, pulse, respiratory rate, oxygen saturation, weight and blood pressure. Height will be measured at screening only.

### **5.3.7 Eastern Cooperative Oncology Group (ECOG) Performance Scale**

The investigator or qualified designee will assess ECOG status (Appendix 1) at screening, prior to the administration of each dose of trial treatment and discontinuation of trial treatment as specified in the study schedule of assessments (Table 3).

### **5.3.8 Pulmonary Function Tests**

Full lung function tests assessments will be performed at screening, prior to the dosing of pembrolizumab (+/- 5 days) and during the maintenance phase of the DLT period as specified in the study schedule of assessments (Table 3).

### **5.3.9 Pregnancy Tests**

Female patients of childbearing potential should have a negative urine or serum pregnancy during screening and within 72 hours prior to receiving the first dose of study medication as specified in the study schedule of assessments (Table 3). If the urine test is positive or cannot be confirmed as negative, a serum pregnancy test will be required.

### **5.3.10 Haematology, Biochemistry and Urinalysis (including, $\beta$ -hCG, PT, aPTT, fT3, fT4 and TSH)**

All Laboratory tests will be performed at screening and then certain assessments at every visit as defined in the schedule of study assessments (Table 3). Sample will be analysed by the local study site laboratory using standard methods for routine tests. Laboratory tests for screening can be performed within 10 days prior to the first dose of treatment. After this all pre-dose laboratory procedures should be conducted no more than 72 hours prior to dosing. Results must be reviewed by the investigator / designee and found to be acceptable prior to each dose of trial treatment. The variables detailed in Table 4 will be measured.

**Table 4:** Required Laboratory Assessments

Haematology	Chemistry	Urinalysis	Other
Haematocrit	Albumin	Blood	PT
Haemoglobin	Alkaline phosphatase	Glucose	aPTT
Platelet count	Alanine aminotransferase (ALT)	Protein	Free triiodothyronine (fT3)
WBC (total and differential)	Aspartate aminotransferase (AST)	Specific gravity	Free thyroxine (fT4)
Red Blood Cell Count	Lactate dehydrogenase (LDH)	Microscopic exam ( If results are abnormal )	Thyroid stimulating hormone (TSH)
Absolute Neutrophil Count	Uric Acid	Urine pregnancy test †	
Absolute Lymphocyte Count	Calcium Corrected		
	Chloride		
	Glucose		
	Phosphate		
	Potassium		
	Sodium		
	Magnesium		
	Total Bilirubin		
	Total protein		
	Blood Urea Nitrogen		
	Creatinine		
	Creatinine Clearance		

† Perform on women of childbearing potential only. If urine pregnancy results cannot be confirmed as negative, a serum pregnancy test will be required.

### 5.3.11 Tumour Imaging and Assessment of Disease

#### 5.3.11.1 Baseline tumour imaging

Imaging should be undertaken to confirm that the patient has disease in the thorax, where lung SBRT is considered appropriate and the lesion is measurable using RECIST v1.1. The scan will also be assessed for an extra-thoracic disease.

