## 1.2 Rationale for the Trial

The abscopal effect refers to a rare phenomenon of tumour regression at a site distant from the primary site of radiotherapy (61). Radiotherapy has been shown to induce abscopal effects in several types of cancer, including melanoma, lymphoma, renal-cell carcinoma and NSCLC (62-65). The effect is attributed to activation of the systemic immune response. Radiation-induced inflammation is known to increase antigen presentation, subsequent tumour recognition, and can ultimately, enhance the tumour-directed immune response (66). This effect may be more pronounced in response to ablative rather than conventional dosage or fractionation schedules (67). More recently, the abscopal effect has been described in the context of patients receiving immunotherapy concurrently with radiotherapy. Formenti *et al* described a case of abscopal response in a patient with advanced NSCLC who received palliative hepatic radiotherapy while on ipilimumab. The response was seen 2.5 months following radiotherapy (68). Experimental data from multiple cancer models have provided sufficient evidence to propose a paradigm shift, whereby some of the effects of radiation are recognised as contributing to systemic antitumor immunity. Therefore, the traditional palliative role of radiotherapy in metastatic disease is evolving into that of a powerful adjuvant for immunotherapy. This combination strategy adds to the current anticancer arsenal and offers opportunities to harness the immune system to extend survival, even among metastatic and heavily pretreated cancer patients (36). Combination trials of immunotherapy and SBRT are required to explore the potential for radiation enhancing the effects of immunotherapy with the aim of improving outcomes for patients with NSCLC (36). The initial step is to assess the tolerability and safety of immunotherapy with SBRT. This clinical trial protocol will look at the safety and tolerability of pembrolizumab, an anti-PD-1 monoclonal antibody, given in combination with lung SBRT in patients with advanced NSCLC.

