### 4.4.1 Inclusion criteria

In order to be eligible for participation in this trial, the patient must:

1. Patients should be  $\geq 18$  years old on the day of signing the informed consent.
2. Patients must have a histological or cytological diagnosis of NSCLC.
3. Patients should have non-radically treatable stage IIIB or IV disease.
4. Patients must have measurable disease as assessed by RECIST v1.1.
5. Patients must have had disease progression or be intolerant of standard first line palliative chemotherapy for non-small cell lung cancer. If they are known to have a driver mutation for which there is a small molecule targeted therapy, they must have had disease progression or be intolerant of this.
6. Patient should have an ECOG performance status 0-1.
7. Patients should be able to tolerate a course of stereotactic radiotherapy as assessed by the investigator.
8. Patients should have disease within the lung, away from critical structures, suitable for treatment to part of a lesion with lung SBRT.
9. Patients must have adequate organ function including MRC dyspnoea score  $<3$  and adequate baseline lung function tests, with an  $FEV_1 > 0.8L$  or  $>30\%$  of predicted and a  $TLCO > 30\%$
10. Demonstrate adequate organ function as detailed in Table 2 (based on bloods within 10 days of C1D1).
11. Have provided tissue from an archival tissue sample or newly obtained tissue sample.
12. Female patient of childbearing potential should have a negative urine or serum pregnancy within 72 hours prior to receiving the first dose of study medication (C1D1). If the urine test is positive or cannot be confirmed as negative, a serum pregnancy test will be required.
13. Female patients of childbearing potential should be willing to use 2 methods of birth control or be surgically sterile, or abstain from heterosexual activity for the course of the study through 120 days

after the last dose of study medication. Patients of childbearing potential are those who have not been surgically sterilized or have not been free from menses for > 1 year.

14. Male patients should agree to use an adequate method of contraception starting with the first dose of study therapy through 120 days after the last dose of study therapy.
15. Be willing to provide informed consent for the trial.

**Table 2:** Adequate Organ Function Laboratory Values. These should be within 10 days of C1D1.

System	Laboratory Value
Haematological	

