### Disease Parameters

**Measurable disease.** Measurable lesions are defined as those that can be accurately measured in at least one dimension (longest diameter to be recorded) as  $\geq 20$  mm by chest x-ray or as  $\geq 10$  mm with CT scan, MRI, or calipers by clinical exam. All tumour measurements must be recorded in millimeters (or decimal fractions of centimeters).

**Malignant lymph nodes.** To be considered pathologically enlarged and measurable, a lymph node must be  $\geq 15$  mm in short axis when assessed by CT scan (CT scan slice thickness recommended to be no greater than 5 mm). At baseline and in follow-up, only the short axis will be measured and followed.

**Non-measurable disease.** All other lesions (or sites of disease), including small lesions (longest diameter  $<10$  mm or pathological lymph nodes with  $\geq 10$  to  $<15$  mm short axis), are considered non-measurable disease. Bone lesions, leptomeningeal disease, ascites, pleural/pericardial effusions, lymphangitis cutis/pulmonitis, inflammatory breast disease, and abdominal masses (not followed by CT or MRI), are considered as non-measurable. ‘Cystic lesions’ thought to represent cystic metastases can be considered as measurable lesions, if they meet the definition of measurability described above. However, if non-cystic lesions are present in the same patient, these are preferred for selection as target lesions.

**Target lesions.** All measurable lesions up to a maximum of 2 lesions per organ and 5 lesions in total, representative of all involved organs, should be identified as target lesions and recorded and measured at baseline. Target lesions should be selected on the basis of their size (lesions with the longest diameter), be representative of all involved organs, but in addition should be those that lend themselves to reproducible repeated measurements. It may be the case that, on occasion, the largest lesion does not lend itself to reproducible measurement in which circumstance the next largest lesion which can be measured reproducibly should be selected. A sum of the diameters (longest for non-nodal lesions, short axis for nodal lesions) for all target lesions will be calculated and reported as the baseline sum diameters. If lymph nodes are to be included in the sum, then only the short axis is added into the sum. The baseline sum diameters

will be used as reference to further characterize any objective tumor regression in the measurable dimension of the disease.

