## **Response Criteria**

### *Evaluation of Target Lesions*

**Complete Response (CR):** Disappearance of all target lesions. Any pathological lymph nodes (whether target or non-target) must have reduction in short axis to <10 mm.

**Partial Response (PR):** At least a 30% decrease in the sum of the diameters of target lesions, taking as reference the baseline sum diameters.

Progressive Disease (PD): At least a 20% increase in the sum of the diameters of target lesions, taking as reference the smallest sum on study (this includes the baseline sum if that is the smallest on study). In addition to the relative increase of 20%, the sum must also demonstrate an absolute increase of at least 5 mm. (Note: the appearance of one or more new lesions is also considered progressions).

Stable Disease (SD): Neither sufficient shrinkage to qualify for PR nor sufficient increase to qualify for PD, taking as reference the smallest sum diameters while on study.

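### The SBRT-treated lesion can count towards RECIST and irRC response, and ORR and DCR are reported with no split between irradiated and non-irradiated disease

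*Combined protocol and SAP*

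**What the plan says.** - **Eligibility (4.4.1).** "Patients must have measurable disease as assessed by RECIST v1.1", and "Patients should have disease within the lung, away from critical structures, suitable for treatment to part of a lesion with lung SBRT". No criterion asks for a measurable lesion outside the radiation field.
- **Baseline imaging (5.3.11.1).** The scan confirms disease in the thorax "where lung SBRT is considered appropriate and the lesion is measurable using RECIST v1.1".
- **RECIST target lesions (Appendix 6, Disease Parameters).** "All measurable lesions up to a maximum of 2 lesions per organ and 5 lesions in total" are taken, and "Target lesions should be selected on the basis of their size (lesions with the longest diameter), be representative of all involved organs". Nothing excludes the irradiated lesion. Partial response is "At least a 30% decrease in the sum of the diameters of target lesions".
- **irRC (Appendix 7).** Partial response is a fall of at least 50% in the sum of products over all index and new measurable lesions, again with no exclusion.
- **Irradiated volume (Appendix 3, item 3).** The GTV may be a whole visible lesion or part of one, up to 3 cm.
- **Analysis (8.1.2).** ORR and DCR are proportions of all treated patients, pooling Parts A and B. A separate yes/no variable records mixed responses, meaning response at some sites with progression at others. It is not tied to the SBRT field.

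**The concern.** Section 1.1.3 credits SBRT itself with high rates of local tumour destruction. The baseline scan is taken before SBRT, so any local shrinkage is counted against the baseline sum. In a patient with one or two measurable lung lesions, the selection rule puts the irradiated lesion in that sum automatically.

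Section 1.2 builds its rationale on regression at sites distant from the radiotherapy and says that "Combination trials of immunotherapy and SBRT are required to explore the potential for radiation enhancing the effects of immunotherapy". A response confined to the irradiated lesion is not evidence of that, yet the planned tables would not distinguish it from a response elsewhere. The confirmation scan at 4 weeks or more tests whether a response persists, not where it occurred. At stake is what the secondary response endpoints can tell the designers of a phase 2 trial.

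**Working it through.** **1. The plan's own figure.** Two dose levels × 6 patients + 12 in expansion = 24, the stated maximum. No ORR target, power or significance level is given, so there is no other figure to reproduce.

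**2. When local shrinkage alone gives a partial response.** Let s be the irradiated lesion's share of the baseline sum of diameters and x its fractional shrinkage, with all other lesions unchanged. The sum falls by s·x, and RECIST PR needs s·x ≥ 0.30, so x ≥ 0.30/s.

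| Share s | Shrinkage needed |
|---|---|
| 100% | 30% |
| 75% | 40% |
| 60% | 50% |
| 50% | 60% |
| 40% | 75% |
| 30% | 100% |
| below 30% | not possible |

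By the same argument, irRC needs the irradiated lesion to be at least 50% of the baseline sum of products.

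**3. Worked cases.** Lesion sizes are assumptions; 30 mm matches the 3 cm GTV limit. Products treat lesions as equal in both diameters.

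- Sole target lesion, 30 to 21 mm: -30.0% by RECIST. Product 900 to 441 mm², -51.0% by irRC. PR on both.
- 30 mm irradiated plus 20 mm not, only the first halving: (15 + 20 - 50)/50 = -30.0%. Product (225 + 400 - 1300)/1300 = -51.9%. PR on both.
- 30 mm irradiated plus 20 and 15 mm not, the first going to 10 mm: -30.8% and -52.5%. PR on both.
- 30 mm irradiated plus 20, 20 and 15 mm not, the first disappearing: -35.3% and -46.8%. PR by RECIST only.
- 30 mm irradiated plus 30 and 40 mm not, the first disappearing: -30.0% and -26.5%. PR by RECIST only, at the 30% limit.

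**4. Masking in DCR.** At the first on-study scan, suppose the irradiated lesion goes from 30 to 15 mm and the other from 20 to 30 mm. The sum is 45 against 50 mm, -10%, which is stable disease and counts as disease control. The product is 225 + 900 = 1125 against 1300 mm², -13.5%, which is irSD. The non-irradiated lesion alone has grown by 10 mm (+50%), past the RECIST progression threshold of 20% and 5 mm. Its product has gone from 400 to 900 mm² (+125%), past the 25% irRC threshold.

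**5. Possible effect on the pooled rate.** Section 1.1.4.2 quotes an ORR of 18.0% for pembrolizumab alone in previously treated patients. Let q be the share of the remaining 82% scored as PR through local shrinkage alone. Then ORR = 0.18 + 0.82q with no systemic gain. The documents give no value for q, so the range is assumed.

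| q | ORR | Expected responders of 24 |
|---|---|---|
| 0 | 18.0% | 4.3 |
| 0.1 | 26.2% | 6.3 |
| 0.2 | 34.4% | 8.3 |
| 0.3 | 42.6% | 10.2 |

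**The case against.** **ORR is not offered as an abscopal test.** This stands. The primary objective is safety and RP2D (2.1.1), Section 1.2 calls safety and tolerability the first step, and ORR and DCR are there to assess clinical benefit of the combination (2.1.2). Shrinkage of an irradiated lesion is part of that benefit. A reader might infer that ORR fails at its stated job; the documents do not support that.

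**Only part of a lesion may be treated.** This weakens the effect, particularly for large lesions, but does not remove it. Appendix 3 also allows the whole lesion to be treated, and Appendix 6 records the diameter of the whole lesion in either case.

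**Patients may have several target lesions.** This also stands in part. Where the irradiated lesion is under 30% of the sum, a RECIST PR needs shrinkage elsewhere. The selection rule already takes in other measurable lesions within its caps, so most patients who have non-irradiated measurable disease will have it in the sum. Nothing planned identifies who they are.

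**The mixed-response variable covers this.** It does not. It requires progression elsewhere, so it misses local shrinkage with stable disease elsewhere, and it leaves ORR and DCR unchanged.

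**The appendix is only a summary.** Appendix 6 calls itself a quick reference to the published criteria. The absence of an exclusion is established for the protocol text, not for that publication.

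**Conclusion.** The point holds for the secondary response endpoints. As written, local shrinkage can be scored as PR when the irradiated lesion is at least 30% of the baseline sum of diameters (at least 50% of the sum of products for irRC). It can also turn growth elsewhere into stable disease. The lesion sizes and q are assumptions; the thresholds are the protocol's own. Combined ORR is a sound description of total response, but it does not isolate response outside the field. DLT, MTD and RP2D are untouched.

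Three stronger readings are tempting but not supported:

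- **DCR is inflated generally.** If non-irradiated disease is unchanged, the patient is already stable and already counted. DCR moves only when local shrinkage masks target-lesion growth. New lesions and unequivocal non-target progression still make RECIST progression.
- **The histology and PD-L1 comparisons are biased upward.** No direction is shown. The chi-squared test between histologies in 8.1.2 is on mixed responses, although 2.2.2 also lists ORR and DCR by histology. Local-only responses occurring equally across PD-L1 groups would more likely blur an association than create one.
- **A planned comparison with the 18-19% background ORR is invalid.** No such comparison is planned. With 24 patients, 4 responders give an exact 95% interval of 4.7% to 37.4%, so a close reading against 18% would not be possible anyway. Step 5 is a caution for anyone who makes that comparison informally.

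**What to change.** 1. Flag the SBRT-treated lesion in the CRF, and record whether the patient has a measurable non-irradiated lesion.
2. State in Section 8.1.2, before analysis, that ORR and DCR by both RECIST and irRC will be reported twice: over all lesions, and with the irradiated lesion removed from the baseline and follow-up sums. Give each its own denominator and confidence interval.

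The work is a lesion flag and one further analysis of scans already scheduled. Treatment, eligibility and sample size do not change. The downside is that patients whose only measurable lesion is irradiated are not evaluable in the second analysis, so its denominator is smaller and its interval wider. Lesion measurements would allow the split to be made afterwards, but prespecifying it avoids a post hoc choice of which lesions to count.
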